1.7 Determination of Sample Size

The sample size required for the MOVE Trial was determined via simulation based on the available WBCT HO volumes from the NHS and the observed efficacy of palovarotene treatment in Phase 2. The NHS will serve as the external control group with, for the purposes of the determination of sample size, the assumption that 45 subjects will have baseline, 1-year, and 1.5-year WBCT HO volumes and 45 subjects will have baseline, 1-year, and 2-year WBCT HO volumes. It is also assumed that approximately 50% of these 90 subjects will enter the Phase 3 study to begin palovarotene treatment.

There are three interim efficacy analyses – with futility analyses at the second and third interim analyses – and a final analysis planned. Assuming a one-sided, overall type I error rate of 2.5%, the Lan-DeMets alpha-spending function with O’Brien-Fleming parameterization was used to determine stopping boundaries (see [Section 0](#) for additional details).

Available pairs of NHS WBCT scans for 65 subjects taken one year apart and read using the original NHS single-reader process were used to tabulate the number of body regions with new HO and the mean and standard deviation (SD) of new HO volume in each body region ([Table 1](#)). The original 15 body regions from the NHS WBCT scans were mapped to approximate the 9 body regions that will be used in the MOVE Trial. The mean (SD) number of body regions with new HO per subject in approximately one year was 0.707 (1.11), i.e., there were 46 body regions with new HO in 65 subjects.

Table 1. NHS WBCT Scan Results by Body Region

Body region	Number of observations	Number of regions with new NO	Proportion of regions with new HO	Volume change given new HO in region (in thousands mm ³)	
				Mean	SD
Neck, upper spine and chest	64	12	0.19	25.83	21.06
Shoulder (left, right)	130	7	0.05	4.69	3.08
Elbow, hand and wrist (left, right)	125	1	0.01	31.27	-
Lower spine and abdomen	65	11	0.17	16.22	19.24
Hip (left, right)	130	9	0.07	81.17	89.65
Knee and distal lower extremity (left, right)	128	6	0.05	9.04	14.64

Simulations to assess power were conducted as follows:

1. A subject-level rate of body regions with new HO were randomly drawn from a gamma distribution with mean = 0.707 and SD = 1.11.

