The new HO volume (square-root of the volumetric increase in that region) in region r , $\sqrt{Z_{ijr}}$, where new HO has occurred for subject i in scan j is assumed to be distributed as:

$$\sqrt{Z_{ijr}}/1000 \sim N\left(\alpha * \alpha_r * \theta_{2,t(ij)}, \frac{\alpha_r^2}{\tau_{t(ij)}}\right).$$

The scale of new HO volume is modeled in the thousands. Letting $\theta_{2,0} = 1$, the variable $\theta_{2,1}$ is the multiplicative effect of palovarotene treatment on the new HO volume conditional on new HO occurring. The α_r are region-specific variables that contribute to the mean of new HO and the variance; the restrictions $\alpha_r = \alpha_{r'}$, where r and r' are a left and right region pair are included, i.e., right chest and left chest, right arm and left arm, right hip and left hip, and right lower leg and left lower leg. The precision variables, τ_0 and τ_1 , introduce flexibility by allowing variability to differ between new HO volume in treated subjects and untreated subjects.

The prior distributions for the variables in the Bayesian compound Poisson distribution are the following:

$$\begin{aligned}\lambda_i &\sim \text{Gamma}(a, \text{scale} = b) \\ \beta_1, \beta_2 &\sim N(0, 2^2) \\ a, b &\sim \text{Gamma}(1, 1) \\ \alpha &\sim N(0, 1) \\ \alpha_r &\sim \text{Unif}(0, 4) \\ \tau_0, \tau_1 &\sim \text{Gamma}(1, 0.01) \\ \theta_{1,1}, \theta_{2,1} &\sim \text{Unif}(0, 2).\end{aligned}$$

All gamma distributions are parameterized as the shape and rate, except as noted for λ_i . The primary efficacy analysis comparing the annualized change in new HO volume between subjects treated with palovarotene and untreated subjects is performed by calculating the ratio of the annual mean change in HO volume in palovarotene treated subjects to untreated subjects using the Principal FAS and assuming missing at random.

In this SAP, new HO is deemed to be present in a body region if the volume of net new HO is greater than zero, i.e., the change in volume of HO in a region between two timepoints is positive. (Volumes of individual lesions are not assessed; the net volume of HO in a body region is reported.). Any regions with amounts of new HO $< 0 \text{ mm}^3$, i.e., reductions in the volume of HO over time (which can happen due to bone remodeling or measurement variability), will be represented as having no new HO and the volumes will be set to zero in the analysis.

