For these reasons, while acknowledging that it is post-hoc, the sponsor believes that the Bayesian compound Poisson analysis without the square-root transformation is the more appropriate analysis of the primary endpoint, relative to the Bayesian compound Poisson analysis with the square-root transformation. The Bayesian analysis without square root transformation is referred to as the analysis of primary interest.

When performed without the square-root transformation, the new HO volume in region r , Z_{ijr} , where new HO has occurred for subject i in scan j is assumed to be distributed as:

$$Z_{ijr}/1000 \sim N\left(\alpha * \alpha_r * \theta_{2,t(ij)}, \frac{\alpha_r^2}{\tau_{t(ij)}}\right).$$

The prior distributions for the variables in this Bayesian compound Poisson distribution are the following:

$$\begin{aligned} \lambda_i &\sim \text{Gamma}(a, \text{scale} = b) \\ \beta_1, \beta_2 &\sim N(0, 2^2) \\ a, b &\sim \text{Gamma}(1, 1) \\ \alpha &\sim N(0, 10^2) \\ \alpha_r &\sim \text{Unif}(0, 4) \\ \tau_0, \tau_1 &\sim \text{Gamma}(1, 100) \\ \theta_{1,1}, \theta_{2,1} &\sim \text{Unif}(0, 2). \end{aligned}$$

The Bayesian compound Poisson model will be fitted using the R statistical computing language and environment. The R programs will be run using v3.5.0 or later; packages used, including version number, will be identified in the CSR.

Additional supportive analyses including the weighted mixed linear effect (wMLE) analysis with and without the square-root transformation will also be performed. The wLME analysis without the square-root transformation was previously the primary efficacy analysis, before the Bayesian compound Poisson analysis was added in Amendment 1 of the protocol. This wLME analysis without square-root transformation is referred to as the alternative analysis of primary interest.

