It must be noted, however, that this analysis does not eliminate the effect of the more frequent assessments in MOVE; as described in the MOVE and NHS Independent Review Charter, radiologists only measured the amount of HO if they first determined there was new HO relative to the previous timepoint. If there was no new HO, the volume from the previous assessment was carried forward. Because the read process for the 12-month timepoint used the 6-month assessment and the read process for the 24-month assessment used the 18-month assessment, this analysis can investigate only the bias introduced by the differences in visit schedules into the analysis, not the differences in visit schedules per se.

In any case, the sponsor believes that the differences in visit schedules could result in biases of the event rate treatment effect $\theta_{1,1}$ against palovarotene and growth rate treatment effect $\theta_{2,1}$ in favor of palovarotene but that, in the absence of the square-root transformation, these biases are offset, yielding an unbiased estimate of $\gamma = \theta_{1,1} * \theta_{2,1}$.

With the square-root transformation, however, the bias against palovarotene in the event rate treatment effect $\theta_{1,1}$ is unchanged, while the bias on growth rate treatment effect $\theta_{2,1}$ in favor of palovarotene is reduced, yielding a bias in γ against palovarotene.

Consider identical growth events in NHS and MOVE of 8000 mm³ that is split across two six-month intervals in the MOVE study as 4000 mm³ in the first 6-month interval and 4000 mm³ in the next 6-month interval. This registers as two events in one year on MOVE, but just one event in NHS. Similarly, the growth rate, conditional on there being an event, is 2X higher in NHS than MOVE, i.e., 8000/4000=2, in the absence of a square-root transformation. With a square-root transformation, however, the growth rate per event is only 1.4X higher in NHS than MOVE, i.e., $\sqrt{8000}/\sqrt{4000} \sim 1.41$.

A similar comparison of analyses will be performed with wLME, where negative values are zeroed out by region and then square-root transformed, because the bias illustrated above from the square-root transformation should also affect this annualized HO endpoint, which is constructed using new HO observed at each visit.

Analyses of Secondary Efficacy Endpoints

Proportion of Subjects with Any New HO (Key Secondary Endpoint) and Number of Body Regions with New HO

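### The Unif(0,2) priors on the two treatment effects are not neutral, and θ1,1 is cut off at the no-effect value of the SAP's own example: a prior sensitivity analysis is needed

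*SAP*

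**What the plan says.** SAP 2.4.4 models the number of body regions with new HO (treatment effect θ1,1) and the volume per affected region (treatment effect θ2,1), and reports γ = θ1,1 × θ2,1. Under Primary Analysis (square-root scale) and again under Additional Analyses (no transformation), both effects have Unif(0,2) priors. The untransformed list opens "The prior distributions for the variables in this Bayesian compound Poisson distribution are the following" and also sets α ~ N(0,10²) and α_r ~ Unif(0,4), with volume in thousands of mm³.

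Under Sensitivity Analyses, the SAP considers the same 8000 mm³ of growth in both studies, split evenly over two six-month MOVE intervals: "This registers as two events in one year on MOVE, but just one event in NHS". From this the sponsor states its belief that, "in the absence of the square-root transformation, these biases are offset, yielding an unbiased estimate of" γ. None of the listed sensitivity analyses varies a prior.

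**The concern.** The argument for preferring the untransformed model is that more frequent MOVE scanning raises θ1,1 and lowers θ2,1 by matching amounts. That requires the model to let θ1,1 rise as far as the data take it. In the SAP's example θ1,1 is 2, which is the edge of its prior, while θ2,1 = 0.5 lies well inside its range. An upward shift is blocked and the downward shift is not, so the offset cannot fully work there.

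The event definition makes a large event ratio possible. Any positive net change in a region since the previous scan counts, and individual lesions are not followed, so continuing growth can be counted at each MOVE scan. At stake is how much of the reported γ and posterior probability comes from the priors rather than the data.

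**Working it through.** **1. The SAP's example.** Event ratio 2/1 = 2. Volume per event, NHS to MOVE, is 8000/4000 = 2, so θ2,1 = 0.5 and γ = 2 × 0.5 = 1. On the root scale √8000/√4000 = 1.41, so γ = 2/1.41 = 1.41. Both SAP ratios are reproduced, and the untransformed no-effect point is θ1,1 = 2, exactly the prior's upper bound.

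**2. Joint prior.** For two independent Unif(0,2) variables, P(γ < g) = (g/4)(1 − ln(g/4)). At g = 1 this is 0.25 × (1 + 1.386) = 0.597.

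**3. Size of the cap effect.** The untransformed model, without covariates and at the final look only, was fitted by MCMC to 600 simulated trials per scenario with true γ = 1. Inputs from SAP 1.7: 90 NHS and 80 MOVE subjects (45 shared), subject rates from a gamma with mean 0.707 and SD 1.11, and Table 1 volumes. A share f of MOVE growth events is split equally over two scans, so true θ1,1 = 1 + f and θ2,1 = 1/(1 + f). The documents do not give f, so the full range is shown; f = 1 is the SAP's example. Cap lifted means an upper limit of 20 for θ1,1. Wider α means SD 1000.

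| f | Median γ, stated priors | Cap lifted | Wider α, cap kept | Both | Null trials above 0.981, stated | Same, cap lifted | Posterior mass of θ1,1 above 2, cap lifted |
|---|---|---|---|---|---|---|---|
| 0 | 1.10 | 1.10 | 1.05 | 1.05 | 0.7% | 0.8% | 0.7% |
| 0.25 | 1.10 | 1.10 | 1.05 | 1.05 | 0.5% | 0.5% | 4.5% |
| 0.5 | 1.06 | 1.10 | 1.01 | 1.05 | 1.2% | 1.0% | 15.8% |
| 0.75 | 1.00 | 1.10 | 0.95 | 1.04 | 2.8% | 1.3% | 34.8% |
| 1 | 0.92 | 1.09 | 0.88 | 1.04 | 6.2% | 1.7% | 56.1% |

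The value 0.981 is the SAP's planning threshold for the final analysis, used here only as a yardstick. Simulation error on these shares is about 1 percentage point. At f = 0.5 the cap changes γ by 1 − 1.06/1.10, about 4%.

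**4. The α prior.** The hip row of SAP Table 1 reads "Hip (left, right) 130 9 0.07 81.17 89.65". The untreated regional mean is α × α_r, at most 4α, so a mean of 81.17 needs α ≥ 81.17/4 = 20.3, or 2.03 prior SDs. The other regions need at most 0.78 SD. The hip mean rests on 9 regions: SE = 89.65/√9 = 29.9, rough 95% interval 23 to 140. In the simulations the posterior median of α was 20 to 21 under the stated prior and 22 to 23 under a nearly flat one, so the data largely override the prior. What remains raises γ by about 5%, against palovarotene. Separate runs with α ~ N(0,100²) agree: median θ2,1 is 1.08 under the stated prior against 1.03 when the truth is 1.0, and 0.53 against 0.50 when it is 0.5.

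**5. A neutral alternative.** Raising the uniform cap is not neutral: Unif(0,20) with Unif(0,2) gives P(γ < 1) = (1/40)(1 − ln(1/40)) = 0.12. A uniform prior on θ also shifts log θ up by about s², where s is the standard error of log θ. With s near 0.2 (assumed) for both effects, that is exp(0.04 + 0.04) = 1.08 on γ. With log θ1,1 and log θ2,1 ~ N(0,1), the prior P(γ < 1) is 0.5. A normal approximation with standard errors of that order keeps the null median γ at 0.98 to 1.01 for every f, against 0.87 to 1.07 under Unif(0,2) and about 1.06 to 1.11 with the cap simply lifted.

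**Limits.** A single final look of the square-root model gave success probabilities of 0.008 and 0.86, against the cumulative 0.021 and 0.922 in SAP Table 2. It omits the interim looks, so it neither reproduces nor contradicts that table.

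**The case against.** **The example is one event.** It does not show that every MOVE event splits, or splits evenly, and the documents give no share. This stands and limits the size: below about three quarters the cap matters little.

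**The prior does not favour palovarotene throughout.** From the 0.60 a reader might infer a general tilt toward benefit. The simulations do not support that: under the stated priors median γ is at or above 1 up to about f = 0.75 and falls below only near complete splitting. Nor is the prior peculiar to the post-hoc analysis, since the square-root model has the same one.

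**The hip is not excluded.** A reader might infer that the α prior contradicts Table 1. It does not: the value is about two prior SDs out, imprecisely estimated, and within reach. A reader might also infer that the α prior became strongly informative when the transformation was dropped. That depends on reading the root-scale model literally as √Z/1000. The SAP also says "The scale of new HO volume is modeled in the thousands", and if √(Z/1000) was meant, the hip needs √81.17/4 = 2.25 prior SDs on that scale too.

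**No decision hangs on it.** SAP 2.4.4 says that thresholds for success and futility no longer apply after the second interim. The percentages above 0.981 are therefore not a trial error rate.

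**Other analyses exist.** The wLME and GEE models have no priors, and the annual-schedule rerun should move θ1,1 away from its bound. They could reveal a large discrepancy. But wLME and GEE are different estimators, and no change of prior is planned for the rerun, so none shows how far the priors moved the reported γ. The separate simulation report mentioned in SAP 1.7 might, but it is not among the documents.

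**The sentence on bias is a stated belief about scan schedules.** Its arithmetic is correct; it takes no account of the bound.

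**Conclusion.** The point holds in limited form. In both Bayesian models the Unif(0,2) priors are not neutral: P(γ < 1) = 0.60 before data, and θ1,1 is truncated at the SAP's own no-effect value while θ2,1 is not. If f is about 0.75 or more, the truncation pulls γ toward benefit; at f = 1 median γ is 0.92 rather than 1.09, and 6.2% rather than 1.7% of null trials pass 0.981. At f ≤ 0.5 it is worth about 4% or less. The α prior is tight for the hip and works in the opposite direction by about 5%.

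The sizes rest on the SAP's planning inputs, an assumed f, equal halves, no covariates and a single look. They were computed for the untransformed model only. They show that the claim of an unbiased γ needs a condition, not that the trial's result is an artefact of its priors.

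**What to change.** Add a prior sensitivity analysis to SAP 2.4.4, covering both scales:

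- log θ1,1 and log θ2,1 ~ N(0,1) in place of Unif(0,2).
- For the untransformed model, also a wider α prior such as N(0,100²). Change the two together: widening α while keeping the cap moves γ further toward benefit (0.88, with 12% of null trials above 0.981, at f = 1).
- Report γ, θ1,1, θ2,1 and P(γ < 1) beside the stated-prior results, with the posterior mass of θ1,1 near 2 under the stated priors.
- Qualify the unbiasedness sentence: the offset does not hold when θ1,1 is near its bound.

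The cost is one extra run of the existing R code for the Bayesian analyses. SAP 2.4.4 plans no Bayesian analyses after database lock, and SAP 3.3 plans no rerun of interim-CSR analyses, so the text should list this as a supplementary run on the third-interim dataset.

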2.1.3 Efficacy Endpoints

Primary Efficacy Endpoint

The primary efficacy endpoint is the annualized change in new HO volume as assessed by low-dose, WBCT, excluding head. The annualized change in new HO volume will be compared between treated and untreated subjects. WBCT scans are performed at baseline, Month 12,

Month 24 and Month 36 in the NHS and at baseline, Month 6, Month 12, Month 18 and Month 24 in the MOVE Trial. WBCT scans may also be performed at the time of early study discontinuation.

As described in the MOVE Trial and NHS Independent Review Charter, HO volume is assessed by two independent readers blinded to study and timepoint, with adjudication by a third independent reader. HO volume is measured by body region with the baseline scan. The following 9 anatomical regions will be used to describe HO location:

- Right chest, neck, shoulder through mid-humerus
- Left chest, neck, shoulder through mid-humerus
- Mid Torso: torso below shoulder regions and above iliac crests
- Right arm: mid-humerus through hand
- Left arm: mid-humerus through hand
- Right hip: iliac crest, hip through mid-femur
- Left hip: iliac crest, hip through mid-femur
- Right lower leg: mid-femur through foot
- Left lower leg: mid-femur through foot

In post-baseline scans, the presence of new HO within each body region and, if present, the HO volume within the body region, are measured. The primary efficacy analysis described in [Section 0](#) models the number of body regions with new HO compared to the previous scan and the volume of new HO within each body region with new HO compared to the previous scan as the unit of measurement.

Note that the primary endpoint includes annualized HO based on the new HO observed up to Month 24 in MOVE and up to Month 36 in NHS. The sponsor believes that the new HO observed between Month 24 and Month 36 in NHS is relevant and that annualization is sufficient to protect against bias. Sensitivity analyses to assess impact of differences in length of follow-up between NHS and MOVE are described in [Section 2.4.4](#).

The primary efficacy endpoint, as well as the secondary endpoints that depend on the efficacy imaging, will not be summarized in the descriptive analysis to be conducted before the first formal interim efficacy analysis, due to the ongoing nature of the blinded reads.

Secondary Efficacy Endpoints

The following secondary efficacy endpoints will be assessed:

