A subject-level random effect will be used to account for the correlation among repeated measures on the same subject as subjects may contribute follow-up from both the NHS and the current study. Baseline HO volume divided by age will be the only covariate included in the model, in addition to the factor identifying study of origin. The LME model will be fitted using only a subject's observations associated with the longest follow-up in the NHS and the current study with weights used to account for the different lengths of observed subject follow-up. Missing at random will be assumed for the primary analysis and no imputation of missing data performed.

The wLME analyses will be run using SAS 9.4 or higher. The code will use the following structure:

```
proc mixed data=data;
    class treat usubjid;
    model annrate_newho = treat basetot_bage /s;
    random usubjid;
    lsmeans treat/pdiff=control('0') cl;
    weight fup;
run;
```

In this code, treat is a binary indicator for study (1=MOVE, 0=NHS); usubjid is a unique identifier of subjects (used across all FOP studies); annrate_newho is the annualized rate of new HO; and fup is follow-up in years.

The Bayesian compound Poisson analysis and wLME analysis without square-root transformation and including all assessments on or before December 4, 2019, for subjects <14 years old on the date of their assessment and assessments on or before January 24, 2020, for all other subjects, will be repeated using the Principal PPS after the third interim analysis.

Descriptive statistics summarizing the total HO by study visit, change in HO volume by study visit, and change in HO volume from baseline by study visit will be provided. Tables summarizing annualized new HO will also be produced. Summaries will also be provided by body region. Summaries of new HO coincident with flare-ups and not coincident with flare-ups will also be generated. Summaries of annualized mean New HO, conditional on new HO volume>0 mm³, will be created. HO listings will also be generated.

Missingness, including frequency of WBCT not collected and regions that are not evaluable, will be summarized. Frequency of negative new HO, i.e., apparent reductions in HO overall and by body region (defined below), will also be summarized.

Handling of Reductions in HO

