Please note that, as referenced above, the Bayesian compound Poisson models with and without square-root transformation assume non-negative changes in HO volume for each subject for each region, and any apparent reductions in HO volume over time (i.e., negative new HO volumes) are “zeroed out”, i.e., replaced with zero. (All analyses of square-root transformed new HO volumes require non-negative new HO volume in order for the square-root transformation to be applied.) In contrast, because wLME is a regression method, it is less specialized and can accommodate the negative values when applied to non-transformed data.

However, in order to understand the relative contributions to the results of 1) zeroing out the negative changes; 2) square-root transformation of the zeroed out new HO volumes; 3) using a body-region or overall whole body based analysis; 4) using data on intervals between WBCTs, not just the first and last timepoint; 5) Bayesian compound Poisson analysis; we will run five wLME “series”:

1. Raw, untransformed data (i.e., including all negative values)
2. Zero out overall whole-body new HO without square-root transformation
3. Zero out overall whole-body new HO with square-root transformation
4. Zero out by region [by visit] without square-root transformation
5. Zero out by region [by visit] with square-root transformation

For series 2 and 3, the sum of new HO at the last timepoint, i.e., changes from baseline including negatives, is added across body regions. If negative, the sum is replaced with zero. For series 3, the sum is square-root transformed. Then the sum – or square-root of the sum – is divided by time in years, resulting in the annualized new HO.

For series 4 and 5, negative changes in HO volume by region (from previous visit) are replaced with 0. For series 5, the square-root of each change is taken. These numbers are then added across timepoints and body regions and their sums are divided by time in years, resulting in annualized new HO. This method for constructing annualized new HO, with and without square-root transformation, yields wLME analyses that are the closest analogs to the Bayesian compound Poisson analyses.

Note that in applying the square-root transformation to zeroed out new HO for intervals, wLME using series 5 should be subject to the same bias as is attributed to the Bayesian compound Poisson primary analysis illustrated later in this section.

Control of Type I Error

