Ninety-nine palovarotene-naïve subjects with the R206H ACVR1 mutation were enrolled into the current trial and are to be followed for 2 years. There were to be three early interim efficacy analyses and one final analysis. Futility was declared at the second interim analysis, but the study continued. The final analysis for Part A will occur when all subjects have completed 2-year follow-up. (Note that, as described, due to the prolonged palovarotene interruption prior to the completion of Part A, IA3 is designated the final analysis.)

The first interim analysis was to take place when approximately 35 MOVE subjects complete 1 year of follow-up with the second and third interim analyses occurring when all subjects in the Principal EP have the opportunity to have complete (i.e., have WBCT data) 12 months and then 18 months of follow-up, respectively. It was assumed that the full NHS dataset will be available at the first interim analysis. The amount of statistical information at each interim analysis can be approximated by the sum of the follow-up in each study divided by the total expected. The total follow-up expected across the NHS and the MOVE Trial is 317.5 years (NHS: 45*1.5 years + 45*2.0 years; MOVE: 80*2.0 years). Assuming eight subjects enroll in the MOVE study per month, the percentage of subject follow-up for each analysis is summarized in Table 7 where values with an asterisk indicate approximate information based on expected accrual rates and total planned accrual in the Principal EP.

Table 7. Observed MOVE Follow-up at Each Planned Analysis

Analysis	Observed MOVE follow-up	Percentage of follow-up available
Interim #1	35 subjects with 12 months *45 subjects with 6 months	66%
Interim #2	*80 enrolled subjects with 12 months *35 subjects with 18 months	80%
Interim #3	*80 enrolled subjects with 18 months *35 subjects with 24 months	92%
Final	80 enrolled subjects with 24 months	100%

Using these percentages, the alpha level threshold used to determine treatment effect significance at each analysis was derived using the Lan-DeMets alpha-spending function with O'Brien-Fleming parameterization and assuming a one-sided, overall type I error rate of 2.5%. The one-sided significance thresholds are 0.0058, 0.0103, 0.0156, and 0.0190 for the first, second and third interim analyses and the final analysis, respectively, in the scenario above.

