3.3 Third Interim Analysis

An informal analysis will occur at the time of the planned third interim analysis. [Table 8](#) lists the efficacy analyses that will be performed at this analysis.

Note that the third interim analysis dataset will also be summarized in the interim MOVE CSR for Study PVO-1A-301 (MOVE Trial) to be included in the palovarotene NDA and MAA for FOP. The efficacy analyses described in [Table 8](#) will be included, in addition to the additional analyses, sensitivity analyses, analyses of secondary efficacy endpoints, and analyses of exploratory endpoints described in [Section 2.4.4](#). Safety analyses in [Section 2.1.4](#), analyses of imaging performance in [Section 2.1.5](#) and analyses of pharmacokinetic endpoints in [Section 2.1.6](#) will also be included. Further analyses may be added, as appropriate.

Further note that analyses included in the interim CSR are not planned to be rerun for the final CSR.

Table 8. Analyses to be Conducted at Interim Analysis #3

Analysis	Method	Cutoff	Trans.	Subset Subjects	Reason
Analysis of primary interest	Bayesian comp. P.	04Dec2019 for subjects <14 y.o., 24Jan2020 for subjects >=14.y.o.	None	All Subjects	Sponsor believes this is the more appropriate Bayesian analysis of efficacy
Alternative analysis of primary interest	wLME	04Dec2019 for subjects <14, y.o., 24Jan2020 for subjects >=14.y.o.	None	All Subjects	Explore if results of Bayesian analysis are consistent with results from simplified approach
Square-root transformation	Bayesian comp.P.	04Dec2019 for subjects <14, y.o.,	Sq. Root	All Subjects	Show inconsistency of results with square-root transformation

		24Jan2020 for subjects ≥ 14 .y.o.			to results without square-root transformation
Alternative method w/ square-root transformation	wLME	04Dec2019 for subjects < 14 , y.o., 24Jan2020 for subjects ≥ 14 .y.o.	Sq. Root	All Subjects	Show that there is also an inconsistency of results with square-root transformation under simplified approach
Include scans after dosing stopped	Bayesian comp. P	All timepoints	None	All Subjects	Explore if results when with only scans done before dosing interrupted are consistent with results using all timepoints
Include scans after dosing stopped and square-root transformation	Bayesian comp.P.	All timepoints	Sq. Root	All Subjects	Protocol-specified primary analysis (ignoring dosing interruptions)

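### wLME series 3 divides the square root of cumulative new HO by years, so it drifts with follow-up length even with no drug effect, and the series 2 versus series 3 contrast mixes the transformation with follow-up

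*SAP*

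**What the plan says.** SAP 2.4.4, under Handling of Reductions in HO, sets out five wLME series so that the contributions of zeroing, the square root, the regional or whole-body basis, the use of intervals and the Bayesian model can be told apart. Series 2 and 3 both sum the change from baseline to the last timepoint over body regions and floor it at zero. Series 3 then takes the root. "Then the sum – or square-root of the sum – is divided by time in years, resulting in the annualized new HO".

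The wLME takes one record per subject and study, from the "observations associated with the longest follow-up in the NHS and the current study". Years of follow-up enter the model as a regression weight; the SAP describes this as "with weights used to account for the different lengths of observed subject follow-up". SAP 2.1.3 says that the endpoint covers "new HO observed up to Month 24 in MOVE and up to Month 36 in NHS", and relies on annualization to deal with the difference.

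Table 8 in SAP 3.3 lists a square-root wLME run at the third interim analysis, with this reason: "Show that there is also an inconsistency of results with square-root transformation under simplified approach". It does not say which series that row uses.

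The SAP does acknowledge a bias from the square root, but a different one: series 5 and the Bayesian square-root model are affected because MOVE growth is split over six-month intervals. It says nothing about follow-up length in series 3.

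**The concern.** Dividing by time puts unequal follow-up on a common scale only if the numerator grows in proportion to time. Cumulative volume does so under the SAP's model. The square root of cumulative volume does not, so two studies with identical disease and no drug effect get different series 3 rates if their follow-up differs.

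Series 2 and series 3 differ by one step, the root, and their comparison is the whole-body test of what that step does. If series 3 moves for a second reason, part of any gap between them would be put down to the transformation when the annualization step produced it. This matters because the SAP prefers the untransformed analysis partly on the argument that the root distorts the comparison. Evidence for that argument should not carry an artefact of its own.

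**Working it through.** **Inputs**
- Subject rates: gamma, mean 0.707 and SD 1.11 per year, then Poisson counts; regions equally likely; gamma volumes with the Table 1 means and SDs (SAP 1.7).
- Planned follow-up: "NHS: 45*1.5 years + 45*2.0 years; MOVE: 80*2.0 years" (SAP 2.4.4).
- MOVE at the third interim analysis (IA3), from Table 7: "80 enrolled subjects with 18 months *35 subjects with 24 months". I read this as 45 at 18 months and 35 at 24 months. The second interim (IA2) row, read likewise, gives 45 at 12 and 35 at 18 months.
- NHS subjects leaving for MOVE: "approximately 50% of these 90 subjects will enter the Phase 3 study" (SAP 1.7).
- NHS mixes other than the planned one are assumptions.

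**1. The plan's own figures.** 45×1.5 + 45×2.0 + 80×2.0 = 67.5 + 90 + 160 = 317.5 years, as stated. √8000/√4000 = 1.41, as stated. The SAP gives no bias figure for series 3.

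**2. Untransformed rate.** Counting left and right sides separately gives ten regions. Mean volume per event is (25.83 + 2×4.69 + 2×31.27 + 16.22 + 2×81.17 + 2×9.04)/10 = 29.44 thousand mm³. Times 0.707 this is about 20.8 thousand mm³ per year, whatever T is. Simulation agrees: about 20,800 at each duration.

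**3. Series 3 rate.** Let S be cumulative new HO over T years and m(T) = E[√S]/T. Simulated with no drug effect, in √mm³ per year:

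| T (years) | 1 | 1.5 | 2 | 3 |
|---|---|---|---|---|
| m(T) | 67.5 | 61.0 | 56.2 | 49.5 |

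A separate run gave 67.4, 60.9, 56.1 and 49.2. Over three years E[√S] rises from 67.5 to 3×49.5 = 148.5, a factor of 2.2 rather than 3.

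**4. Study means.** With weight T, a study's mean is Σ n·T·m(T) / Σ n·T.
- MOVE, IA3 mix: (67.5×61.0 + 70×56.2)/137.5 = 58.56
- MOVE, all at 24 months: 56.2
- MOVE, IA2-like mix: (45×67.5 + 52.5×61.0)/97.5 = 64.0
- NHS, planned: (67.5×61.0 + 90×56.2)/157.5 = 58.26
- NHS, half at 24 and half at 36 months: (2×56.2 + 3×49.5)/5 = 52.18
- NHS, all at 12 months: 67.5; all at 36 months: 49.5

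**5. MOVE/NHS ratio with no drug effect** (above 1 means that MOVE looks worse)

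| MOVE | NHS | Ratio |
|---|---|---|
| IA3 mix | planned | 58.56/58.26 = 1.005 |
| all 24 months | planned | 56.2/58.26 = 0.965 |
| IA3 mix | half 24, half 36 | 58.56/52.18 = 1.12 |
| IA3 mix | all 36 | 58.56/49.5 = 1.18 |
| IA2-like mix | all 12 | 64.0/67.5 = 0.95 |
| IA2-like mix | planned | 64.0/58.26 = 1.10 |
| IA2-like mix | all 36 | 64.0/49.5 = 1.29 |

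The separate run moves these by at most about 0.01. Reading the SD of 1.11 as that of the counts, dropping heterogeneity between subjects, or changing the region mix gives 1.14 to 1.19 for IA3 against all-36-month NHS.

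**6. Weighting.** The weight changes how much a record counts, not its expectation. It can shift the result: for the IA3 mix against NHS in equal thirds at 12, 24 and 36 months, the ratio is 1.07 weighted and 1.02 unweighted.

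**7. Candidate repairs.** With equal windows the ratio is 1.00. Putting the division inside the root, √(S/T), reverses the bias: for 24 against 36 months, 56.2×√2 / (49.5×√3) = 79.5/85.7 = 0.93.

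**The case against.** The strongest objection concerns size and reach. From the Month 24 and Month 36 limits, a reader might infer that series 3 makes MOVE look worse by a fixed amount, say a tenth. The documents do not support that. Month 36 is a maximum for NHS, about half of the NHS subjects were expected to transfer to MOVE, and SAP 2.4.4 says most who left NHS did so to enter an interventional study, so many NHS records may be short. Under the planned follow-up the bias is close to nil at IA3 and slightly favours MOVE at 24 months. This stands: the mechanism is certain, but no single percentage is.

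A reader might also infer that the SAP's whole case about the transformation is confounded. That is not supported either. The visit-schedule comparison in SAP 2.4.4 uses the by-region form, series 5. That form adds roots interval by interval, so it does not shrink with total follow-up in this way. Table 8 names no series, so its square-root wLME row is affected only if it uses series 3.

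Third, the consequence is limited. The series are post-hoc diagnostics, success and futility thresholds no longer apply, and both analyses of primary interest are untransformed. That also stands, and it keeps the point away from the efficacy conclusion.

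What does not stand is any suggestion that existing analyses cover it. The restrictions to 15 and 27 months sit under a heading aimed chiefly at the untransformed analysis, and they cap follow-up without equalising it.

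**Conclusion.** The point holds for series 3 and for the series 2 versus series 3 contrast. The series 3 rate depends on follow-up length when there is no drug effect, and it disadvantages the study with the shorter follow-up. Under the SAP's generator the null ratio runs from about 0.965 to 1.18 for the Table 7 third-interim and final MOVE mixes, against NHS follow-up from planned to all at 36 months. For an IA2-like MOVE mix, probably nearer to the December 2019 and January 2020 dosing cutoffs, it runs from about 0.95 to 1.29 as NHS goes from all at 12 to all at 36 months.

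These figures rest on the planning model, on Table 7's planned counts of 80 rather than the 99 enrolled, and on assumed NHS follow-up. They are weighted means; I expect the mixed model to fall between the weighted and unweighted results. Since neither size nor sign can be fixed from the documents, the contrast cannot be read as the effect of the square root alone. The correction is worth making, but it concerns a supportive analysis.

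**What to change.** Keep the five series as planned and add an equal-window version of all five: baseline to Month 12 in both studies and, separately, baseline to Month 24 where both scans exist, with no division by unequal time. Changing only series 2 and 3 would confound their comparison with series 1, 4 and 5 by window length. Base any statement about the square root in the whole-body analysis on the equal-window version, and state in Table 8 which series its square-root wLME row uses. Do not substitute √(S/T), whose bias runs the other way.

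The added version will not remove the interval-splitting effect in series 5, which the SAP already discusses. It should be labelled post hoc. The SAP does not plan to rerun interim-report analyses for the final report, so this would be a new supportive run.

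The cost is a short SAP addition and wLME reruns on scans already read. Scans outside the common windows go unused in those runs, and few MOVE subjects may reach Month 24 before the dosing cutoff, so the Month 12 window would carry most of the information.
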